As a final step, we will develop a **longitudinal model to characterize CoASY mRNA expression profiles over the entire 24-month study treatment period**. We plan to use a mixed effects model with random intercept and slope to account for correlation between measurements and to allow individuals to vary from the group mean. We will explore a number of possible parameterizations of the time effect, including fractional polynomials and splines. We will allow for different trajectories by (a) dose group and (b) PKAN type in separate models with a group x time interaction. This model will take the general form $CoASY_{ij} = \beta_0 + \beta_1 t_{ij} + \beta'_2 group + \beta_3 t_{ij} \times group + b_{1i} + b_{2i} t_{ij}$, where t_{ij} represents time on treatment in months (including partial months as decimals) and group indicates dose group or PKAN type, depending on the model.

Latent growth curve modeling plan for the exploratory aim will not be described here but is described in full in the protocol.

1. Protocol Title: A phase 2 study of a vitamin metabolite in PKAN

2. Objectives

The primary objective of this study is to assess the safety and tolerability of 4'-phosphopantetheine (4'-PPT), a product of intermediary metabolism, in pantothenate kinase-associated neurodegeneration (PKAN), an inborn error of vitamin B5 metabolism. The study product meets the FDA statutory definition for consideration as a medical food and is being developed as such for the nutritional management of PKAN.

The primary hypothesis is that there will be no clinically significant difference in safety or tolerability profiles between active and placebo groups during six months of double-blind parallel study, nor between dose groups over up to 18 months of treatment with 4'-PPT.

The primary aims are:

- To compare safety or tolerability profiles of 4'-PPT between active and placebo groups over the 6-month double-blind parallel group phase of the study; and
- To examine the long-term safety and tolerability profile of the compound over up to 18 months of open-label period.

The primary endpoints are:

- Safety outcome measures will include treatment-emergent adverse events and abnormalities on standard laboratory tests collected over up to 24 months of treatment.
- Tolerability outcomes will be assessed via participant retention in the study and adherence to the study product regimen.

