Because this clinical trial is being conducted remotely, every effort will be made to ensure that participants complete at least the scheduled safety labs and telephone visits within the study visit windows. A participant-specific schedule of visit dates will be generated at enrollment, and study staff will send visit reminders via phone calls or emails in advance of scheduled blood draws. Per-participant compliance will be closely tracked: participants will not be allowed to complete more than 3 required visits more than 7 days out of window over the life of the study, with a 'required' visit defined as one involving safety lab blood draw and / or adverse event assessment. If compliance drops below this standard during the double-blind phase, the Primary Cohort participant will be terminated from the study, and required to be re-screened and re-randomized as a new participant in order to re-enroll in the study. If compliance drops below this standard during the open-label phase, the study product supply will be suspended but the Primary Cohort or Open-label Cohort participant will still be considered enrolled in the study and ongoing attempts will be made to have the participant complete assessments. If the participant subsequently succeeds in completing the most recent set of missed assessments, study product supply and dosing may be resumed. A repeat episode of non-compliance with the study schedule during the open-label phase will result in the participant's termination from the study. Exceptions may be made on a case-by-case basis, with the input of the medical monitor, DSMB and IRB as needed.

If the participant elects to withdraw from the study prematurely, or if the investigator and / or the participant's medical providers feel it is in the participant's best interests to withdraw from the study early, a Primary Cohort participant will be asked to complete the Month 24 and Month 25 activities and an Open Label participant will be asked to complete the Month 18 and Month 19 activities, if possible. The reason for premature withdrawal will be recorded. Every effort will be made to ensure any remaining study product is returned to the study site.

f. Unscheduled visits

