Comparisons of participants experiencing treatment-emergent adverse events and abnormalities on clinical labs will be reviewed for clinical significance in the Safety Analysis dataset, which includes all participants in the primary cohort who consume at least one dose of the study product. Events expected as part of the usual disease course in PKAN, whether present at trial enrollment or not, will not be considered or captured as adverse events.

Frequencies of participants experiencing at least one adverse event (AE) will be displayed by body system and preferred term according to *Medical Dictionary for Regulatory Activities* (MedDRA) terminology. Detailed information collected for each AE will include a description of the event; duration; whether the AE meets criteria as a Serious Adverse Event (SAE); severity / grade of the event; relationship to study product; changes made to the study product in response to the event; and clinical outcome. Severity of the AEs will be graded according to the NCI *Common Terminology Criteria for Adverse Events*, Version 4.0^[15]. If the event meets criteria as an SAE, the nature of the SAE will be classified according to standard FDA criteria.

The number and percentage of patients who experienced any serious AE (SAE), treatment-emergent AE, and treatment-emergent SAE will be summarized, as well as the total number of events per arm. AE data will be presented for months 0-6, 7-25 and cumulatively, as appropriate. Emphasis in the analyses will be placed on AEs classified as treatment-emergent.

Clinically-significant abnormalities on clinical labs will be tabulated similarly to AEs. The number and percentage of patients experiencing clinically-significant abnormalities will be compiled in summary tables to examine the distribution by collection month [0-1-3-6-7-9-12-18-24 +/- 25 months for the Primary Cohort; and 0-1-3-6-9-12-18 +/- 19 for the Open-label Cohort].

Graphic displays may be provided to illustrate the results over time. Initial review of group differences and determination of clinical significance will be performed by an unaffiliated physician familiar with the study population and blinded to treatment arm.

Tolerability Analysis

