We will assess the success of blinding in at six months, before unblinding, by asking participants or their proxies to which treatment allocation they think they were assigned. Possible responses will fall in five categories of "Strongly believe the treatment is active", "Somewhat believe the treatment is active", "Somewhat believe the treatment is placebo", "Strongly believe the treatment is placebo" and "Don't know." We will calculate and compare blinding

eIRB 18782 CoA-Z in PKAN (NIH)

indices (BI) in each arm using the method of Bang et al. We will not use statistical inference testing because of the limited size of the study.

11. Privacy, Confidentiality, and Data Security

As noted, most participants will be recruited from those in our established repository (eIRB 7232) and our PKAN natural history study (eIRB 10832). Only participants who have already provided consent to be re-contacted about future research opportunities will be contacted. Other potential subjects may contact our team after seeing an IRB-approved post about the study on our website, via clinicaltrials.gov, or other means. When any potential participants are reached by phone, if they feel they do not have sufficient privacy, study staff will offer to call them back at a better time. Study staff will not leave any sensitive information in messages left on voicemail.

Consent phone calls will be pre-arranged at a designated time when potential participants can ensure their privacy. Following the consent discussion, a secure link to the online consent form in REDCap Cloud will be sent via the OHSU email system. Rarely, a paper consent form will instead be mailed for signatures with a return envelope. Participants being seen at OHSU for clinical care will be consented face-to-face in a private exam room at OHSU.

All study visits will be done remotely by phone. Again, if a participant feels they do not have sufficient privacy, study staff can offer to call them back at a later time that day. Safety labs and research blood samples will be collected by a designated lab local to each subject. In most cases, samples will be collected at Quest clinical draw stations that meet standard privacy requirements. A small number of participants in more remote locations may have blood collected at their local physician's clinical offices, which should provide a similar level of privacy.

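### The early-exit procedure has no double-blind version, so a participant who leaves before Month 6 is not asked for the remaining safety assessments of the randomised comparison

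*Combined protocol and SAP*

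**What the plan says.** Section 8.e (Suspension of Study Product / Early termination) sets the exit procedure. It begins "If the participant elects to withdraw from the study prematurely" and also covers withdrawal that the investigator or the participant's own medical providers judge to be in the participant's interest. In each case "a Primary Cohort participant will be asked to complete the Month 24 and Month 25 activities", where possible, and the reason is recorded. Month of exit and phase of the trial make no difference.

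The same section treats non-compliance with the visit schedule differently by phase. In the double-blind phase "the Primary Cohort participant will be terminated from the study, and required to be re-screened and re-randomized as a new participant". In the open-label phase product is suspended, but the "participant will still be considered enrolled in the study and ongoing attempts will be made to have the participant complete assessments".

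The first primary aim (Section 2, and the synopsis) is to compare safety or tolerability "between active and placebo groups over the 6-month double-blind parallel group phase of the study". Section 10.b presents AEs for months 0-6 separately from later months, and tabulates clinically significant lab abnormalities to "examine the distribution by collection month". The Safety Analysis dataset keeps every Primary Cohort participant who took at least one dose. Section 10.e says: "We will assess the success of blinding in at six months, before unblinding".

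**The concern.** The randomised evidence on safety ends at Month 6, so follow-up to Month 6 matters most for that aim. People who leave because of poor tolerability may be those most likely to have a later event or a lab change that resolves slowly. Section 8.e does not ask them for the Month 3 or Month 6 assessments still due.

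The primary hypothesis is that the arms do not differ in any clinically significant way. The summaries are numbers and percentages of participants with an event, so a leaver with no event by close-out counts as event-free, although only part of the six months was observed. If such exits were commoner on active product, the missed events would favour the hypothesis. A missing-data method is named only for the exploratory growth-curve aim (Section 10.c), and none for the safety comparison.

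A second question is where the close-out data go. Section 8.e identifies these visits only by the names Month 24 and Month 25. If they were tabulated under those nominal months, data from a few weeks of blinded treatment, possibly placebo, would fall outside the months 0-6 window and sit beside data from long active exposure.

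**Working it through.** **The plan's own figure.** Section 7.a wants 60 participants to complete the double-blind phase, with 5% loss: 60 / (1 - 0.05) = 63.2, rounded up to 64. This reproduces the stated 64. The 4 dropouts are 4/64 = 6.25% of those enrolled. With 1:1:1:1 allocation, 64/4 = 16 are randomised per arm: 16 placebo and 48 active. The figure of 15 per arm is the completer target.

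**What a leaver at Month 2 provides.** The Schedule of Activities for the Primary Cohort has AE evaluation and safety labs at Months 1, 3 and 6 of the double-blind phase. The Month 24 set contains the metabolic profile, blood count, product reconciliation and AE review. The Month 25 set adds a later AE and medication check, with labs optional (Section 8.d). Section 8.e does not state when these take place; I assume close-out at exit and the last contact one month later. Observation then ends at Month 3, and 6 - 3 = 3 double-blind months are lost. The Month 6 lab is lost, and so is the Month 3 lab unless the close-out lab stands in for it.

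**Loss within an arm** (16 x 6 = 96 person-months):

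| 4 planned dropouts, exit at Month 2 | Person-months lost per affected arm | Month 6 labs lost |
|---|---|---|
| All in one arm | 4 x 3 = 12; 12/96 = 12.5% | 4/16 = 25% |
| One in each arm | 1 x 3 = 3; 3/96 = 3.1% | 1/16 = 6.25% |

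**Loss over the whole trial** (64 x 6 = 384 person-months). If exit times are instead uniform over months 0-6, with a last contact one month after exit, the expected loss per leaver is the integral of (5 - t)/6 from 0 to 5, which is 25/12 = 2.08 months. For 4 leavers that is 8.3 person-months, or 8.3/384 = 2.2%. The maximum is 4 x 5 = 20, or 5.2%.

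**Effect on the risk difference.** If a leaver's six-month event status is unknown, the best-to-worst-case range of the active-placebo difference widens by (placebo unknown)/16 + (active unknown)/48:

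- 1 placebo, 3 active: 1/16 + 3/48 = 12.5 points
- 4 active: 4/48 = 8.3 points
- 4 placebo: 4/16 = 25 points

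These are upper limits, because a leaver who has already had the event is already counted.

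**Effect on precision.** At an assumed 20% event rate the 95% half-width is 1.96 x sqrt(0.2 x 0.8 x (1/16 + 1/48)) = 22.6 points. With 15 and 45 it is 23.4 points. The change is small: the issue is which participants are unobserved, and not how many.

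**The non-compliance route.** Termination needs more than 3 required visits, each more than 7 days out of window, where a required visit involves safety labs or AE assessment. After baseline, the double-blind phase has three such visits: Months 1, 3 and 6. Four late visits cannot be reached by then unless screening or baseline counts, so this route adds nothing in practice to the loss above.

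**The case against.** The best defence is that the rule is narrower and more useful than it first appears. It applies to withdrawal from the study, not to stopping product. Month 24 and Month 25 activities name a close-out set that gathers AEs and labs around exit, adds a later contact, and allows repeat labs after an abnormal result. Someone who leaves because of an AE is already counted as having one. Everyone dosed stays in the Safety Analysis dataset, and retention by arm, annotated with exit reasons (Sections 10.b and 10.d), is itself a tolerability outcome. More exits on active product would therefore show. People who withdraw altogether may also refuse further calls.

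All of this stands, and it limits the loss. It does not supply the Month 3 and Month 6 assessments. It also applies less to participants withdrawn on the investigator's or a provider's judgement, who may be willing to continue calls and blood draws.

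Three stronger readings are tempting and not supported:

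- **That stopping product in the double-blind phase means leaving the study.** No section says so. Section 10.b records changes to product in response to an AE, which foresees them. The documents are silent on whether such a participant continues to Month 6.
- **That leavers are put off until calendar Month 24, or that their data are filed there.** The natural reading is a close-out at exit, and collection month can equally mean the month the sample was drawn. Misfiling is a risk left open by the wording, not a stated rule.
- **That termination and re-randomisation for late visits empties the double-blind phase.** The visit count above makes this practically unreachable before Month 6.

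The blinding question is not part of the exit activities, so early leavers are not asked it. That is minor, because the index is descriptive.

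**Conclusion.** The concern holds in a limited form. The plan has one exit procedure for all 24 months, does not separate stopping product from leaving the study, and does not ask a participant who leaves before Month 6 for the remaining double-blind safety assessments. The randomised comparison can therefore lose informative follow-up, though only the part after close-out and the later contact.

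The 12.5% and 25% figures are the extreme case; an even spread, or the trial-wide figure, gives a loss of a few percent. All rest on the planned 4 dropouts and on assumed exit and contact times. Bias towards no difference is possible but depends on who leaves and why, which the documents cannot settle. The labelling of close-out data is a gap to close, not a demonstrated error. The change is worth making because it protects the first primary aim at little cost.

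**What to change.** For the double-blind phase:

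1. Separate stopping product from withdrawing from the study. Ask participants who stop or are taken off product, and who agree, to continue the scheduled phone AE assessments and safety labs through Month 6. Analyse them in their randomised arm. The open-label suspension rule in Section 8.e already uses this idea: "the study product supply will be suspended but the Primary Cohort or Open-label Cohort participant will still be considered enrolled in the study".
2. For those who leave entirely, define an early-termination visit with its own name and timing. Record its date, and tabulate its labs and AEs by actual date and phase.
3. Ask the blinding question at that visit.
4. Show stopping product and leaving the study separately in the retention table. Section 10.d currently reports adherence and study exit, and has no row for stopping product while remaining enrolled.

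The cost is mainly protocol and consent wording, since the calls and local blood draws are already in the schedule. The downside is a few off-product visits. Some participants will decline, so the loss will shrink but may not reach zero.

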Therefore, this study will be conducted using a novel, home-based approach that will minimize the risks of travel to participants, reduce the burden to families, and contain the costs of trial execution. Study assessments (mainly adverse event evaluation) will be conducted via scheduled telephone or OHSU approved teleconferencing service. Blood draw kits for safety and biomarker labs along with return mailers will be sent to participants and arrangements made with a local lab or provider for blood draw. Participant height and weight will be obtained at set intervals throughout the study for dose calculation. Study product will be shipped to participants and left-over product returned by the participant via pre-paid mailer for product accountability / compliance assessment. With participants' consent, local clinical providers will be notified of their patient's participation in the study and provided contact information for the trial investigators, whom they will be encouraged to contact with any concerns at any point in the study.

While this long-distance approach is unconventional and would not be appropriate for a high-risk drug intervention, it is justified in this study because of the low toxic potential posed by 4'-PPT, a normal metabolic constituent of the body being used at doses intended to mimic physiologic levels. The patient and family community have enthusiastically endorsed the trial design and plan for study conduct.

e. Recruitment Methods

OHSU is the leading center in the world for research and clinical care for PKAN and other genetic disorders of brain iron accumulation. Most participants in this trial will be recruited from those in our established PKAN research registry / data and specimen repository (eIRB 7232) who have consented to be contacted for future research opportunities. Most registrants are also active participants in our PKAN natural history study (eIRB 10832) and many are known to us clinically. The clinical trial will be posted on the clinicaltrials.gov website. We will also develop informational and trial recruitment materials for dissemination by the patient advocacy organization and via our own website NBIACure.org prior to study launch: these materials will be submitted for IRB approval in a future modification to this protocol.

f. Consent Process / Modifications to the Consent Process

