The Baseline visit will be conducted by phone. Concomitant medications, adverse events, study product dosing and administration, and instructions for the visit 1 and 2 blood draws will be reviewed with the participant. The timing of the first product administration will be mutually confirmed between the participant and the study staff; this will determine the study schedule going forward. Participants will be instructed in the logistics and importance of getting safety and biomarker labs drawn on schedule, completing the dosing diary, documenting the timing and nature of any adverse events, and returning left-over study product at the end of each dosing period as each new batch of product is received.

c. Follow-up visits

Follow-up visits will be conducted by phone, with the timing and activities as detailed in the Schedule of Activities table on p. 23-26. Study product, blood draw kits and pre-paid return shipping materials for return of study product will be sent to the participant at intervals throughout the study. The timing and frequency of study product shipments will be dictated not only by the study schedule but also likely by FDA feedback on stability data from the ongoing shelf-life studies. Participants will always receive more study product than needed to supply them to the next shipment date or study visit date to ensure there is no interruption in dosing due to shipment delays. Study staff will arrange for the blood draws and height / weight measurement with a CLIA-certified lab local to the participant's home as per the Schedule of Activities. Participants will return left-over study product to the study site using pre-paid shipping materials at the end of each dosing interval as new product is received.

d. End-of-study visit

The Primary Cohort participants will take their final dose of study product at Month 24 visit, ideally on the same day as the Month 24 scheduled blood draw for safety and biomarker labs. A final study visit will take place at Month 25 (+ 1 month window allowed for final follow up); at a minimum, this will include AE and Concomitant Medications assessment; safety and / or biomarker labs may be added at investigator discretion, for example if any safety lab value at the Month 24 visit shows clinically significant abnormalities or if a sample was compromised.

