An unscheduled visit may be conducted at investigators' discretion at any point in the study in response to an adverse event or other clinically-significant event. Such a visit will always include assessment of adverse events and concomitant medications; safety labs and biomarker labs may be added at the investigator's discretion.

eIRB 18782 CoA-Z in PKAN (NIH)

Schedule of Activities for Primary Cohort Participants

Procedures Primary Cohort	Screening#	Baseline#	Visit 1	Visit 2	Visit 3	Visit 4	Visit 5	Visit 6	Visit 7	Visit 8	Visit 9	Visit 10	Visit 11
	Month -2	Month 0	Month 0 + 3 days +/- 2d	Month 1 +/- 5d	Month 3 +/- 5d	Month 6 -10 to 0d	Month 6 + 3 days +/- 2d	Month 7 +/- 5d	Month 9 +/- 5d	Month 12 +/- 5d	Month 18 +/- 5d	Month 24 +/- 5d	Month 25 + 1 month/- 5d
Informed Consent	X												
Demographics	X												
Medical history / Confirmation of PKAN diagnosis	X												
Randomization	X												
Complete metabolic profile ^{A,B}	X			X	X	X		X	X	X	X	X	
CBC with differential ^B	X			X	X	X		X	X	X	X	X	
Biomarker labs ^B	X		X	X		X	X			X			X
Height / Weight ^C	X					X				X	X	X	
Study product reconciliation				X	X	X		X	X	X	X	X	
Concomitant Medications Log	X	X		X	X	X		X	X	X	X	X	X
Evaluate for Adverse Events		X		X	X	X		X	X	X	X	X	X

eIRB 18782 CoA-Z in PKAN (NIH)

A = Standard CMP includes Na⁺, K⁺, Cl⁻, CO₂, BUN, Creat, Ca²⁺, Glu, Alb, T. Protein, Alk Phos, T. Bili, AST, ALT. CK may be ordered separately.

B= If a technical error occurs drawing, running, or shipping a lab, it may need to be repeated. Minor variations in safety lab components allowable at PI discretion.

C= Height and weight will be measured more frequently at the PI's discretion for children based on age and apparent growth rate

An unscheduled visit may be conducted at investigators' discretion at any point in the study in response to AE or other clinically-significant event. Such a visit will include AE assessment and concomitant medications assessment. Safety labs and biomarker labs may be added at investigator discretion. For subjects who are hospitalized, were recently discharged, or are too sick to leave home for safety labs, it is acceptable to use clinical labs collected up to 14 days before or after the study window.

eIRB 18782 CoA-Z in PKAN (NIH)

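### The 14-day allowance for outside clinical labs has no Month 6 exception, so a lab drawn after the apparent switch to open-label product can be filed as the blinded Month 6 value

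*Combined protocol and SAP*

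**What the plan says.** The Primary Cohort Schedule of Activities places safety labs at Months 1, 3 and 6 of the blinded phase, then at Month 7 and later in the open-label phase. Months 1, 3 and 7 have windows of plus or minus 5 days. Month 6 is different: "Month 6 -10 to 0d". The Open-label Cohort, which has no change of treatment, uses plus or minus 5 days at its own Month 6. The next Primary Cohort visit is "Month 6 + 3 days +/- 2d".

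A footnote to the same schedule relaxes the windows for participants who are hospitalized, recently discharged or too ill to leave home for labs: "it is acceptable to use clinical labs collected up to 14 days before or after the study window". No visit is excluded.

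On the timing of the switch, section 8.b says of the first dose that "this will determine the study schedule going forward". Section 8.e adds: "A participant-specific schedule of visit dates will be generated at enrollment". Section 10.b has the placebo group starting treatment after month 6. No text gives the day of the first open-label dose, and none holds that dose until the Month 6 assessments are done.

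On analysis, section 10.b (Safety Analysis) says clinically significant lab abnormalities are "compiled in summary tables to examine the distribution by collection month", with 6 and 7 as adjacent categories. Section 10.d lists individual safety events by measure and time point. Neither section assigns a lab according to the product being taken when it was drawn.

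**The concern.** The one-sided window and the footnote work against each other. The window appears designed so that Month 6 is sampled on blinded product. The footnote then reopens the two weeks after it for the participants whose labs are most likely to be abnormal.

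Lab abnormalities are part of the primary safety endpoint (section 2), and the placebo comparison lasts only six months. If a placebo participant has already moved to active product, a lab drawn in those two weeks reflects some days on active product but may be tabulated as placebo Month 6. An abnormality caused by the product would then count against placebo and narrow the contrast that the trial is meant to describe. Participants who started on 5 or 20 mg/m² also change dose at the switch, so their Month 6 entries can be misfiled by dose in the same way.

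Judgment at the time of review cannot be relied on to catch this. Under section 10.e the study team stays blinded to assignment throughout, and under section 10.b the physician judging clinical significance is blinded to arm. A rule based on dates would work without unblinding anyone.

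**Working it through.** There is no planned figure to reproduce. The check is window arithmetic plus the weight of one participant.

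**Inputs**
- Month 6 window: day −10 to day 0, where day 0 is the scheduled end of Month 6 (Primary Cohort schedule).
- Month 7 and Month 3 windows: plus or minus 5 days (same schedule).
- Allowance: 14 days on either side of the window (footnote).
- Arm size: 15 evaluable, or 64/4 = 16 enrolled (section 10.a).
- Assumption: the first open-label dose falls at about day 0.

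**Days accepted for Month 6**
- Earliest: −10 − 14 = −24. Latest: 0 + 14 = +14.
- Total: 25 days (−24 to 0) + 14 days (+1 to +14) = 39 days.
- Days after the window closes: 14 of 39 (36%). This is a count of calendar days, not a probability that a lab falls there.

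**Sensitivity to the switch day.** If the first open-label dose falls on day s (0 ≤ s ≤ 14), the accepted days after it number 14 − s:
- s = 0: 14 days
- s = 5: 9 days
- s = 14: none

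**Overlap with Month 7**
- 30-day month: earliest accepted day for Month 7 = 30 − 5 − 14 = +11, so days +11 to +14 qualify for both visits.
- 28-day month: 28 − 5 − 14 = +9, overlap +9 to +14.
- 31-day month: 31 − 5 − 14 = +12, overlap +12 to +14.

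**Is Month 6 the only blinded visit affected?** The latest accepted day for Month 3 is about 90 + 5 + 14 = 109 days after first dose, well short of Month 6, and Month 1 ends earlier still. So among the three post-dose blinded lab visits, only Month 6 has an allowance that can cross a change of treatment.

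**Weight of one misfiled lab**
- 1/15 = 6.7 percentage points of the arm's Month 6 column.
- 1/16 = 6.25, or 6.3 points.

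**The case against.** The strongest reply is that the premise is inferred. Section 10.e assesses blinding at six months, before unblinding. The dose depends on body surface area (section 6), and section 7.d says "Participant height and weight will be obtained at set intervals throughout the study for dose calculation". Height and weight are due at Month 6 and are arranged together with the blood draw, so a participant too ill for labs may not have been measured for the new dose either. If the switch waits for the visit, the gap closes. This stands as a real limit on the concern. It does not settle the matter, because no text makes the switch wait, and the schedule is fixed from the first dose.

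Second, a participant who missed the window through illness was often ill before day 0, on blinded product. Moving that lab to the open-label phase could blame active product for an illness that began on placebo. This is a fair point, and the fix needs a flag for it.

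Third, collection month could mean the actual month of the draw, and adverse event records separately capture duration, relatedness and product changes. Both help, but the categories listed are the scheduled visit months, and the footnote exists so that an off-schedule lab can stand in for a scheduled one. The text is ambiguous at best.

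Fourth, safety is judged on clinical rather than statistical significance. That is correct, so no test result is at risk.

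A reader might also take section 8.e, under which "participants will not be allowed to complete more than 3 required visits more than 7 days out of window", as accepting late samples as Month 6 data. It does not: it is a compliance rule, and it does not say which phase a sample belongs to.

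**Conclusion.** The gap is real but narrow. Followed literally, the footnote lets a lab drawn on open-label product fill the blinded Month 6 slot, and it makes about days +11 to +14 valid for two visits in different phases with nothing to choose between them. That is a conflict between two stated rules and deserves correction.

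Harm requires several things together: a participant ill at that time, a switch already made, the later lab being the one used for Month 6, and an abnormality that arose after the switch. The documents give no rate of hospitalization or lateness, so the number affected is unknown and probably very small. Each case would be 6.3 to 6.7 points of an arm.

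Two stronger readings are not supported. One is that the primary safety comparison is compromised: the switch day is inferred, the exposure is limited to a few ill participants, and the review is descriptive. The other is that the CoASY analysis of placebo participants starting treatment is contaminated by this footnote. The allowance is for clinical labs standing in for safety labs and does not cover biomarker samples.

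The conclusion assumes that open-label dosing starts at about Month 6. The later it starts after day 0, the smaller the gap.

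**What to change.** Add to the footnote of the Primary Cohort Schedule of Activities: *At the Primary Cohort Month 6 visit, the 14-day allowance covers only labs collected before the first open-label dose.*

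Add to section 10.b, Safety Analysis: *Labs are assigned to the double-blind or open-label phase by draw date relative to the first open-label dose. A lab drawn after that dose is tabulated as open-label, with a flag if the related illness began before it.*

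With a first open-label dose at day 0, the accepted range for Month 6 becomes day −24 to day 0 and the overlap with Month 7 disappears. The flag deals with illness that started on blinded product. No visit is added, the compliance rule in section 8.e is untouched, and there is no need to prolong blinded dosing or to re-time Visit 5.

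The cost is an occasional missing Month 6 lab value. For example, a placebo column with no abnormalities would read 0/14 instead of 0/15. The exact upper 95% limit, 1 − 0.025^(1/n), would rise from 1 − 0.025^(1/15) = 21.8% to 1 − 0.025^(1/14) = 23.2%. That is a small loss compared with a value recorded under the wrong treatment.
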